5.3 Data Abstraction

In addition to the medical record data abstraction described in Section 4.3 (demographics, diagnosis, standardized intensity of treatment rating), the study team will abstract detailed data regarding the patient's medical history and therapeutic exposures (e.g., names of surgeries, chemotherapy, radiation, and related dates), according to the *Children's Oncology Group's Cancer Treatment Summary Form* (see Appendix 7; modified version applies to patients enrolled after 3-1-16),¹³² including details such as cumulative doses of selected chemotherapy, radiation, and immunosuppressive agents; and if applicable, date and type of HCT; presence and extent of chronic GvHD; and dose and duration of selected immunosuppressive agents post-HCT.

5.4 Vaccination Protocol

5.4.1

Quadrivalent HPV Vaccine (for patients enrolled on or before 3-1-16): The qHPV vaccine (HPV-6, -11, -16, -18 vaccine, recombinant; Gardasil®; Merck Research Laboratories) is a non-infectious recombinant quadrivalent vaccine prepared from the purified virus-like particles (VLPs) of the major capsid (L1) protein of HPV types 6, 11, 16, and 18. The L1 proteins are produced by separate fermentations in recombinant *Saccharomyces cerevisiae* and self-assembled into VLPs. The fermentation process involves growth of *S. cerevisiae* on chemically-defined fermentation media which include vitamins, amino acids, mineral salts, and carbohydrates. The VLPs are released from the yeast cells by cell disruption and purified by a series of chemical and physical methods. The purified VLPs are adsorbed on preformed aluminum-containing adjuvant (Amorphous Aluminum Hydroxyphosphate Sulfate). The quadrivalent HPV VLP vaccine is a sterile liquid suspension that is prepared by combining the adsorbed VLPs of each HPV type and additional amounts of aluminum-containing adjuvant and the final purification buffer.

Each 0.5 ml dose of the vaccine contains approximately 20 mcg of HPV 6 L1 protein, 40 mcg of HPV 11 L1 protein, 40 mcg of HPV 16 L1 protein, and 20 mcg of HPV 18 L1 protein. The vaccine also contains approximately 225 mcg of aluminum (as amorphous aluminum hydroxyphosphate sulfate adjuvant), 9.56 mg of sodium chloride, 0.78 mg of L-histidine, 50 mcg of polysorbate 80, 35 mcg of sodium borate, less than 7 mcg yeast protein/dose, and water for injection. The vaccine does not contain preservatives (including thimerosal) or antibiotics.

Nonavalent HPV Vaccine (for patients enrolled after 3-1-16): The 9vHPV vaccine (HPV-6, -11, -16, -18, -31, -33, -45, -52, -58) vaccine, recombinant; Gardasil®9; Merck Research Laboratories) is a non-infectious recombinant nonavalent vaccine prepared from the purified virus-like particles (VLPs) of the major capsid (L1) protein of HPV types 6, 11, 16, 18, 31, 33, 45, 52, and 58. The L1 proteins are produced by separate fermentations in recombinant *Saccharomyces cerevisiae* and self-assembled into VLPs. The fermentation process involves growth of *S. cerevisiae* on chemically-defined fermentation media which include vitamins, amino acids, mineral salts, and carbohydrates. The VLPs are released from the yeast cells by cell disruption and purified by a series of chemical and physical methods. The purified VLPs are adsorbed on preformed aluminum-containing adjuvant (Amorphous Aluminum Hydroxyphosphate Sulfate). The nonavalent HPV VLP vaccine is a sterile liquid suspension that is prepared by combining the adsorbed VLPs of each HPV type and additional amounts of aluminum-containing adjuvant and the final purification buffer.

Each 0.5 ml dose of the vaccine contains approximately 30 mcg of HPV 6 L1 protein, 40 mcg of HPV 11 L1 protein, 60 mcg of HPV 16 L1 protein, 40 mcg of HPV 18 L1 protein, 20 mcg of HPV Type 31 L1 protein, 20 mcg of HPV Type 33 L1 protein, 20 mcg of HPV Type 45 L1 protein, 20 mcg of HPV Type 52 L1 protein, and 20 mcg of HPV Type 58 L1 protein. The vaccine also contains approximately 500

mcg of aluminum (as amorphous aluminum hydroxyphosphate sulfate adjuvant), 9.56 mg of sodium chloride, 0.78 mg of L-histidine, 50 mcg of polysorbate 80, 35 mcg of sodium borate, less than 7 mcg yeast protein/dose, and water for injection. The vaccine does not contain preservatives (including thimerosal) or antibiotics.

5.4.2 Vaccine Supply and Storage

HPV vaccine for this study will be dispensed from a single lot (or if not possible due to expiration dates, from subsequent similar lots) by Merck Research Laboratories to the Investigational Pharmacist at each participating site. The Pharmacist at each site is required to maintain complete records of all study vaccines received from Merck Research Laboratories and subsequently dispensed, discarded, or returned. All unused vaccines must be destroyed on-site at the Investigational Pharmacy after the study is completed or terminated. Damaged or expired study vaccines are to be handled in the same manner.

The vaccine should be kept refrigerated at 2°C to 8°C (36°F to 46°F), protected from light, and should not be frozen. Any vaccine that becomes inadvertently frozen must be discarded.

Additional storage considerations for 9vHPV vaccine: The 9vHPV vaccine should be administered as soon as possible after being removed from refrigeration. The 9vHPV vaccine can be administered provided total (cumulative multiple excursion) time out of refrigeration (at temperatures between 8°C and 25°C) does not exceed 72 hours. Cumulative multiple excursions between 0°C and 2°C are also permitted as long as the total time between 0°C and 2°C does not exceed 72 hours. These are not, however, recommendations for storage.

5.4.3 Vaccine Preparation and Administration

The qHPV and 9vHPV vaccines are supplied in 0.5 ml single-dose vials. The vaccine vial should be agitated thoroughly immediately prior to administration to obtain a uniform suspension. After thorough agitation, the vaccine appears as a white, cloudy suspension. The vaccine should be used as supplied. No dilution or reconstitution is necessary. The vaccine should not be mixed in the same syringe or injected at the same site as other vaccines, and should not be injected intravenously or intradermally.

0.5 ml of the vaccine should be withdrawn from the single-dose vial using a sterile needle and syringe free of preservatives, antiseptics, and detergents. The vaccine should be administered intramuscularly in the deltoid region of the upper arm (preferred site) preferably in the nondominant arm, or in the higher anterolateral area of the thigh (if the deltoid site is contraindicated). A 22 to 23 gauge needle long enough to ensure intramuscular deposition of the vaccine should be used, based on the patient’s gender, weight, and site of administration (see Table 4 for preferred needle lengths). As with all vaccines, a solution of 1:1000 epinephrine will be available for injection should an anaphylactic reaction occur.

Table 4. Preferred needle length based on patient gender, weight, and administration site

Gender	Weight	Deltoid: Needle length	Anterolateral Thigh: Needle Length
Male or female	<60 kg	5/8" to 1"	All patients: 1 to 1-1/2"
Male or female	60-70 kg	1"	
Female	>70-90 kg	1" to 1-1/2"	
Male	>70-118 kg	1" to 1-1/2"	
Female	>90 kg	1-1/2"	
Male	>118 kg	1-1/2"	

5.4.4 Vaccine Administration Schedule

Each participant will receive three doses of HPV quadrivalent vaccine (HPV-6, -11, -16, -18; Gardasil®; Merck & Co, Inc.; patients enrolled on or before 3-1-16) or the 9vHPV vaccine (HPV-6, -11, -16, -18, -31, -33, -45, -52 and -58; Gardasil®9; Merck Research Laboratories; patients enrolled after 3-1-16), according to the FDA-recommended 3-dose schedule: Dose #1: Day 1; Dose #2: 8 weeks after first

dose; Dose #3: 24 weeks after first dose. All attempts should be made for participants to receive vaccine at the designated time points (Day 1, Week 8, Week 24). Vaccine should not be given sooner than the following required minimum time intervals between doses: Dose 1 to Dose 2: 8 weeks; Dose 2 to Dose 3: 16 weeks. Acceptable windows for vaccine administration are indicated in Table 5. If vaccine administration is delayed, participants should continue on study and an attempt should be made to delay subsequent vaccine visits, if possible, while maintaining the acceptable windows. For example, if vaccine Dose #2 is delayed from Week 8 to Week 12, all subsequent visits should be delayed by 4 weeks, if possible, so that vaccine Dose #3 will occur at Week 28 (Week 24 + 4 weeks), and the 4-week post-vaccine Dose #3 visit will occur at Week 32 (Week 28 + 4 weeks) and so on, while maintaining the acceptable windows for vaccine administration and laboratory studies specified in Tables 5 and 6.

Table 5: Acceptable windows for vaccine administration

Interval	Dose 1	Dose 2	Dose 3
Minimum interval between vaccine doses	--	8 weeks	16 weeks
Maximum interval between vaccine doses	--	12 weeks	24 weeks
Acceptable vaccine administration window	Day 1	8-12 weeks after Dose 1	24-32 weeks after Dose 1, but no sooner than 16 weeks after Dose 2

5.4.5 Concurrent Therapies

Medications that may interfere with evaluation of the safety and tolerability of the vaccine should not be administered during the indicated timeframes unless medically necessary. Medications in this category include:

- Any live attenuated vaccine administered within 28 days before or after any HPV vaccine injection
- Any subunit or killed vaccines (e.g., influenza, pneumococcal, antigen injections for allergy treatment) within 14 days before or after any HPV vaccine injection

All vaccines and immunosuppressive agents (e.g., corticosteroids, calcineurin inhibitors) taken within 28 days of Dose #1, between Doses #1 and #2, between Doses #2 and #3, and 28 days after Dose #3 will be elicited by the study team and recorded on the Vaccine Visit Form (Appendix 8; completed at Dose 1, Dose 2, and Dose 3) or the Month 7 Visit Form (Appendix 9, completed at Month 7) and if applicable, on the Premature Study Discontinuation (PSD) Form (Appendix 10, completed at PSD visit or at declaration of loss to follow-up, see Section 5.4.13).

5.4.6 Laboratory Studies

Quantitative immunoglobulins: A 6 ml blood specimen for Quantitative Ig (immunoglobulin subsets), collected in a tube supplied by the institution's laboratory, will be drawn on Day 1 (prior to the first vaccine dose). Specimens for Quantitative Ig will be processed and run in the CLIA-approved clinical laboratories at each participating institution and the results reported to the coordinating center.

Anti-HPV -6, -11, -16, -18 (4cLIA; for patients enrolled on or before 3-1-16): A 10 ml blood specimen will be obtained in a non-additive, non-serum separator (non-SST) red top tube on Day 1 and at Months 7 and 24 (designated time windows in Table 6) to measure serum neutralizing antibodies to the 4 vaccine types (HPV-6, -11, -16, -18) using competitive Luminex immunoassays (cLIA). Geometric Mean Titers (GMT) for anti-HPV-6, -11, -16, -18 responses will be reported in milli-Merck Units per milliliter (mMU)/ml.^{133,134}

Anti-HPV -6, -11, -16, -18, -31, -33, -45, -52, -58 (9cLIA; for patients enrolled after 3-1-16): A 10 ml blood specimen will be obtained in a non-additive, non-serum separator (non-SST) red top tube on Day 1 and at Months 7 and 24 (designated time windows in Table 6) to measure serum neutralizing antibodies to the 9 vaccine types (HPV-6, -11, -16, -18, -31, -33, -45, -52, -58) using competitive Luminex immunoassays (cLIA). Geometric Mean Titers (GMT) for anti-HPV-6, -11, -16, -18, -31, -33, -

45, -52, -58 responses will be reported in milli-Merck Units per milliliter (mMU)/ml.^{133,134}

HPV-specific total immunoglobulins: HPV-specific total immunoglobulins (9 IgG) testing will be done using the same 10 ml specimen collected for Anti-HPV-6, -11, -16, -18 (for patients enrolled on or before 3-1-16) or for Anti-HPV-6, -11, -16, -18, -31, -33, -45, -52, -58 (for patients enrolled after 3-1-16) at the Month 24 time point only.

Specimens for Anti-HPV (4cLIA or 9cLIA) and HPV-specific total immunoglobulins (9 IgG) will be processed immediately, frozen, and subsequently shipped on dry ice to UAB where they will be stored frozen and batch-shipped to the PPD Vaccines and Biologics Laboratory, Merck Laboratory, and/or Focus Diagnostics Laboratory. Refer to Appendix 11 for detailed instructions regarding specimen collection, labeling, processing, shipping, and storage. Samples will be tested at PPD Vaccines and Biologics Laboratory, Merck Laboratory, and/or Focus Diagnostics Laboratory in 4cLIA or 9cLIA and 9IgG assays for immunogenicity measurements, and data results will be transferred on quality assured CD. After testing, samples will be stored at PPD Vaccines and Biologics Laboratory, Merck Laboratory, and/or Focus Diagnostics Laboratory at -20°C or lower for 3 months.

Table 6: Acceptable windows for laboratory studies

Study Time Point	Day 1	Month 7	Month 24
Acceptable window when laboratory studies can be drawn	Day 1	4-8 weeks after Vaccine Dose #3	72-84 weeks after Vaccine Dose #3
Studies to be drawn	Quantitative Immunoglobulins (Quant Ig); Anti-HPV (4cLIA for patients enrolled on or before 3-1-16; 9cLIA for patients enrolled after 3-1-16)	Anti-HPV (4cLIA for patients enrolled on or before 3-1-16; 9cLIA for patients enrolled after 3-1-16)	Anti-HPV (4cLIA for patients enrolled on or before 3-1-16; 9cLIA for patients enrolled after 3-1-16); HPV-specific total immunoglobulin (9 IgG)
Specimen requirement	6 ml in tube supplied by institution's clinical lab 10 ml in non serum-separating (non-SST) red top tube	10 ml in non-SST red top tube	10 ml in non-SST red top tube

5.4.7 Vaccine Dose #1 (Day 1)

5.4.7.1 Participants will be provided with education regarding HPV and the HPV vaccine using the most recent versions of the Centers for Disease Control (CDC) fact sheet as posted at www.cdc.gov/std/hpv/STDFact-HPV.htm or other age- and sex-appropriate materials from the CDC, such as materials posted at www.cdc.gov/vaccines/teens or www.cdc.gov/vaccines/who/teens/vaccines/hpv.html (samples in Appendix 12) and the most recent version of the Gardasil® (for patients enrolled on or before 3-1-16) or Gardasil®9 (for patients enrolled after 3-1-16) Vaccine Information Statement (VIS) as posted at www.cdc.gov/vaccines/pubs/vis/default.htm (sample in Appendix 13).

5.4.7.2 Sexually active female participants of childbearing potential will be instructed to use contraception beginning with first vaccine dose and continuing until at least 4 weeks after all 3 vaccine doses have been administered. Participants will be queried prior to each dose to determine if there is a possibility of pregnancy. If there is any possibility of pregnancy, a pregnancy test (urine or blood as per local institutional preference and procedures) will be obtained prior to vaccine administration and if positive, the vaccine will be withheld and the participant withdrawn from receiving further vaccine on the study. The vaccine will not be administered to sexually active females who refuse contraception.

5.4.7.3 The following blood specimens will be drawn:
- Quantitative immunoglobulins (6 ml whole blood in tube supplied by institution's

clinical laboratory) – this specimen will be processed and analyzed by the clinical laboratories at the participating institution and results will be submitted to the coordinating center.

- Anti-HPV: 4cLIA for patients enrolled on or before 3-1-16; 9cLIA for patients enrolled after 3-1-16 (10 ml whole blood in non SST red top tube)
- Specimens (other than for Quantitative immunoglobulins) will be processed and shipped to the coordinating center according to the instructions in Section 5.4.6. and Appendix 11.

5.4.7.4 Targeted review of systems/ screening for acute illness and medication review will be performed. Vaccine administration must be rescheduled if any of the following are present:

- Serious active infection (afebrile upper respiratory infection is not considered a serious infection)
- Fever $\geq 100^{\circ}\text{F}$ or $\geq 37.8^{\circ}\text{C}$ (oral) within 24 hours prior to the visit
- Receipt of any vaccines within 2-4 weeks prior to visit (as per Section 5.4.5)
- Receipt of any blood products or transfusions within 3 months prior to visit
- If acute or chronic medical or surgical conditions or contraindications not described above are present, the site investigator should consult with the coordinating center PI to obtain clearance to administer the vaccine

Vaccine Visit Form (Appendix 8) will be completed and submitted.

5.4.7.5 HPV Vaccine Dose #1 (Gardasil® for patients enrolled on or before 3-1-16; Gardasil®9 for patients enrolled after 3-1-16) will be administered (0.5 ml IM per instructions in Section 5.4.3). Syncope has been reported following vaccine administration and may result in falling with injury; participant will be observed for 30 minutes following vaccine administration to assess for any adverse reactions. As with all vaccines, a solution of 1:1000 epinephrine will be available for injection in the event an anaphylactic reaction were to occur.

5.4.7.6 Participant will be provided with a Vaccine Report Card Kit (thermometer, metric tape measure, and Vaccine Report Card [adverse events diary]) and asked to record oral temperature 4 hours after the vaccine injection and then daily for 5 days following vaccine administration, and to record any adverse symptoms in the diary daily for 7 days (for patients enrolled after 3-1-16) or 14 days (for patients enrolled on or before 3-1-16) post vaccine administration (Appendix 14). The patient or parent/caregiver will be instructed to report any unusual reactions immediately; participants reporting any grade 3 or higher symptoms will be instructed to return to the clinic within 24 hours for evaluation and management. An Adverse Events/Research-Related Problems Reporting Form (AERF – Appendix 15) will be completed and submitted for all adverse events or unanticipated problems requiring expedited reporting (as defined in Section 9.3.2).

5.4.7.7 **For patients enrolled on or before 3-1-16:** Study team member will contact patient (or parent/caregiver) 2 to 3 days following vaccine administration (if unable to reach, regular attempts will continue to be made to contact the patient or parent/caregiver on business days up to 1 week post visit), and again 2 weeks (preferred timeframe: 15-20 days) following vaccine administration (if unable to reach, regular attempts will

continue be made to contact the patient or parent/caregiver on business days up to 3 weeks post visit and then weekly thereafter),to evaluate for any vaccine-related complications. If the patient or parent/caregiver does not respond, they will be asked to provide the information from their Vaccine Report Card at the next scheduled study visit. Data may continue to be collected outside of the suggested timeframes, if necessary. Each item on the Vaccine Report Card form (Appendix 14) will be reviewed with the patient or parent/caregiver and the information recorded by the study team member onto the electronic Vaccine Report Card form within the study database. The Vaccine Report Card completed by the study team member during the follow-up contacts, will be submitted to the study coordinating center via database export. An Adverse Events/Research-Related Problems Reporting Form (AERF – Appendix 15) will be completed and submitted to the coordinating center for all adverse events or unanticipated problems identified during these contacts that meet criteria for expedited reporting (as defined in Section 9.3.2) within 2 business days of becoming aware of the event/problem .

For patients enrolled after 3-1-16: The patient (or parent/caregiver) will be instructed to contact their healthcare provider (and, when feasible, notify the study team) should they experience any severe symptoms (as defined on the Vaccine Report Card) within 2 weeks of vaccine receipt. A study team member will contact the patient (or parent/caregiver) one week (i.e., Day 8, or the first business day after Day 8) following vaccine administration (if unable to reach, regular attempts will continue to be made to contact the patient or parent/caregiver on business days up to 2 weeks post visit) to evaluate for any vaccine-related complications. If the patient or parent/caregiver does not respond, they will be asked to provide the information from their Vaccine Report Card at the next scheduled study visit. Data may continue to be collected outside of the suggested timeframes, if necessary. Each item on the Vaccine Report Card form (Appendix 14) will be reviewed with the patient or parent/caregiver and the information recorded by the study team member onto the electronic Vaccine Report Card form within the study database. The Vaccine Report Card completed by the study team member during the follow-up contact, will be submitted to the study coordinating center via database export. An Adverse Events/Research-Related Problems Reporting Form (AERF – Appendix 15) will be completed and submitted to the coordinating center for all adverse events or unanticipated problems identified during this contact that meet criteria for expedited reporting (as defined in Section 9.3.2), within 2 business days of becoming aware of the event/problem.

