3.3 Exclusion Criteria: Aim 2 (Vaccine Evaluation)

- 3.3.1 Allergy to any component of the HPV vaccine including yeast and aluminum
- 3.3.2 Thrombocytopenia (platelet count <50K) or coagulation disorder that would contraindicate intramuscular injection
- 3.3.3 Transfusion of blood products or intravenous immune globulin within 3 months of study entry
- 3.3.4 Female, and a) currently pregnant or lactating, or b) of childbearing potential and unwilling to avoid pregnancy during the vaccine phase of study (beginning at Day 1 and continuing until at least 4 weeks after all 3 vaccine doses have been administered).

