5.4.8 Vaccine Dose #2

Note: this visit must be conducted no less than 8 weeks after Vaccine Dose #1, and no later than Week 12

5.4.8.1 Sexually active female participants of childbearing potential will be instructed to use contraception beginning with first vaccine dose and continuing until at least 4 weeks after all 3 vaccine doses have been administered. Participants will be queried prior to each dose to determine if there is a possibility of pregnancy. If there is any possibility of pregnancy, a pregnancy test (urine or blood as per local institutional preference and procedures) will be obtained prior to vaccine administration and if positive, the vaccine will be withheld and the participant withdrawn from receiving further vaccine on the study. The vaccine will not be administered to sexually active females who refuse contraception.

- 5.4.8.2 Targeted review of systems/ screening for acute illness and medication review will be performed. Vaccine administration must be rescheduled if any of the following are present:
- Serious active infection (afebrile upper respiratory infection is not considered a serious infection)
 - Fever $\geq 100^{\circ}\text{F}$ or $\geq 37.8^{\circ}\text{C}$ (oral) within 24 hours prior to the visit
 - Receipt of any vaccines within 2-4 weeks prior to visit (as per Section 5.4.5)
 - If acute or chronic medical or surgical conditions or contraindications not described above are present, the site investigator should consult with the coordinating center PI to obtain clearance to administer the vaccine.

Vaccine Visit Form (Appendix 8) will be completed and submitted.

The most recent version of the Gardasil® (for patients enrolled on or before 3-1-16) or Gardasil ®9 (for patients enrolled after 3-1-16) Vaccine Information Statement (VIS), as posted at www.cdc.gov/vaccines/pubs/vis/default.htm (sample in Appendix 13), will be given to the patient/parent.

- 5.4.8.3 HPV Vaccine Dose #2 (Gardasil® for patients enrolled on or before 3-1-16; Gardasil ®9 for patients enrolled after 3-1-16) will be administered (0.5 ml IM per instructions in Section 5.4.3). Syncope has been reported following vaccine administration and may result in falling with injury; participant will be observed for 30 minutes following vaccine administration to assess for any adverse reactions. As with all vaccines, a solution of 1:1000 epinephrine will be available for injection in the event an anaphylactic reaction were to occur.

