5.4.10 Month 7: 4-8 Weeks Following Final Vaccine Dose

Note: this visit must be conducted no earlier than 4 weeks and no later than 8 weeks after Vaccine Dose #3

5.4.10.1 The following blood specimens will be drawn:

- Anti-HPV 4cLIA for patients enrolled on or before 3-1-16 or 9cLIA for patients enrolled after 3-1-16: 10 ml whole blood in non-SST red top tube

Specimens will be processed and shipped to the coordinating center according to the instructions in Section 5.4.6. and Appendix 11.

5.4.10.2 Month 7 Visit Form (Follow-Up #1; Appendix 9) will be completed and submitted.

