5.4.11 Month 24: 72-84 Weeks (~ 2 Years) Following Vaccine Dose #1

Note: this visit must be conducted no less than 72 weeks and no later than 84 weeks after Vaccine Dose #3.

5.4.11.1 The following blood specimens will be drawn:

- Anti-HPV 4cLIA for patients enrolled on or before 3-1-16 or 9cLIA for patients enrolled after 3-1-16, and HPV-specific total immunoglobulin (9 IgG): 10 ml whole

blood in non-SST red top tube

Specimens will be processed and shipped to the coordinating center according to the instructions in Section 5.4.6. and Appendix 11.

5.4.11.2 Month 24 Visit Form (Follow-Up #2; Appendix 16) will be completed and submitted.

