6.7 Financial Obligations and Compensation

There is no charge for participation in this study. Vaccines and related preparation and administration charges and all study-related labs will be provided without cost to the participant. To compensate Aim 2: Vaccine Evaluation participants for their time and transportation expenses related to study participation, participants will receive \$100 (or equivalent voucher/gift card) at Month 7 and \$75 (or

equivalent voucher/gift card) at Month 24.

6.8 **Informed Consent Process**

Informed consent will be obtained from each patient (of age of majority) according to the approved procedures of the institutional review board (IRB) or Ethics Committee at each participating institution. Consent of the parent/guardian and assent of the patient will be obtained for each minor participant according to the policies and procedures in place at each participating institution and according to the laws in the state where the informed consent is being signed. The original consent form will be placed in the medical record. A copy will be given to the participant and a copy will be filed with the research record.

7.0 **CRITERIA FOR EVALUATION AND ENDPOINT DEFINITIONS**

7.1 **Evaluable Patients**

Aim 1 (Survey): A subject will be considered evaluable if they complete the survey item indicating HPV vaccine initiation/non-initiation and for whom medical record abstraction data is submitted as described in Section 4.3.

Aim 2 (Vaccine Evaluation): A subject will be considered evaluable for the primary (immunogenicity) aim if they are seronegative for HPV-16 and/or HPV-18 at baseline, complete all 3 HPV vaccine doses within the specified administration windows (Section 5.4.4), have evaluable Month 7 Anti-HPV 4cLIA (for patients enrolled on or before 3-1-16) or 9cLIA (for patients enrolled after 3-1-16) results that were drawn within the acceptable window (Section 5.4.6), and for whom medical record abstraction data is submitted as described in Section 5.3. Safety data will be reported on all eligible subjects who receive at least one dose of vaccine, regardless of whether they are evaluable for the additional study aims.

7.2 **Primary Endpoints**

Aim 1 (Survey):

1. HPV vaccine non-initiation

Aim 2 (Vaccine Evaluation):

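### Blood products and immune globulin are screened up to Dose 1, but from then to the titre draws no rule requires recording them or removes affected samples from the per-protocol set

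*Combined protocol and SAP*

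**What the plan says.** **Before Dose 1.** Exclusion 3.3.3 rules out "Transfusion of blood products or intravenous immune globulin within 3 months of study entry". Section 5.4.7.4 then reschedules Dose 1 for "Receipt of any blood products or transfusions within 3 months prior to visit". The Dose 1 line does not name immune globulin; only 3.3.3 does.

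**At Doses 2 and 3.** The rescheduling lists in 5.4.8.2 and 5.4.9.2 repeat the Dose 1 items on infection, fever and recent vaccines. The last specific item in each is "Receipt of any vaccines within 2-4 weeks prior to visit (as per Section 5.4.5"). A general clause follows, as at Dose 1: "If acute or chronic medical or surgical conditions or contraindications not described above are present, the site investigator should consult" the coordinating center. Blood products do not appear.

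**At the draws.** For Month 7 (5.4.10), "this visit must be conducted no earlier than 4 weeks and no later than 8 weeks after Vaccine Dose #3". For Month 24 (5.4.11), "this visit must be conducted no less than 72 weeks and no later than 84 weeks after Vaccine Dose #3". Each section gives a time window, a blood draw and a form, and sets no condition on these products.

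**Recording.** Section 5.4.5 covers "All vaccines and immunosuppressive agents (e.g., corticosteroids, calcineurin inhibitors) taken within 28 days of Dose #1", then the intervals between doses, and ends 28 days after Dose 3.

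**Analysis sets.** Section 7.1 requires baseline seronegativity for HPV-16 and/or -18, that subjects "complete all 3 HPV vaccine doses within the specified administration windows (Section 5.4.4), have evaluable Month 7 Anti-HPV" results drawn in window, and abstracted records. The per-protocol definition in 8.2.2.1 is similar. Neither mentions blood products or immune globulin. The Month 24 comparison in 8.2.2.4 uses per-protocol subjects.

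**The concern.** The plan screens for these products before the baseline sample, and nothing equivalent protects the samples that carry the endpoint. If a product holds anti-HPV antibody, a subject who receives it after Day 1 can complete three in-window doses, give an in-window Month 7 sample and count as per-protocol with a titre that is partly donor antibody. Passive antibody can only raise a titre, so any error favours non-inferiority. Under the recording rule as written, the analyst need not even hold the data to find or remove such samples.

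**Working it through.** **1. The rules side by side**

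| Stage | Blood products / immune globulin |
|---|---|
| Entry (3.3.3) | Both excluded within 3 months |
| Dose 1 (5.4.7.4) | Blood products or transfusions within 3 months reschedule the dose |
| Dose 2 (5.4.8.2) | No item |
| Dose 3 (5.4.9.2) | No item |
| Month 7 and Month 24 draws (5.4.10, 5.4.11) | No condition |
| Recorded agents (5.4.5) | Not listed |
| Evaluable and per-protocol sets (7.1, 8.2.2.1) | No condition |

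**2. Timing.** Dose 3 falls 24-32 weeks after Dose 1 (Table 5), and the Month 7 draw 4-8 weeks after Dose 3 (Table 6). The Month 7 draw is therefore 24+4 = 28 to 32+8 = 40 weeks after Dose 1. The Month 24 draw is 24+72 = 96 to 32+84 = 116 weeks after Dose 1. A look-back at Dose 1 covers none of that time. The recording period stops at 28 days after Dose 3, while the Month 7 draw may be at 8 × 7 = 56 days, leaving up to 28 days unrecorded even for the agents that are listed.

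**3. Stratum sizes, used below as denominators.** Table 7 gives stratum maxima of 72, 77, 82 and 81, which sum to 312 as stated. A one-sample, one-sided t-test at alpha 0.00312 and 80% power, with Table 7's E and SD, gives 70 + 79 + 79 + 80 = 308, within 1.3% of 312. The point does not depend on this figure.

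**4. Primary outcome (GMT ratio).** The documents give neither a passive titre nor a frequency of use. Assume that P = 20 to 100 mMU/ml is added in a fraction f = 5% to 10% of subjects, each with a titre T at half the healthy value, in a stratum whose true ratio is 0.50. The ratio then reads 0.50 × ((T+P)/T)^f.

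- Younger females, HPV-16: T = 4918.5/2 = 2459.25. The ratio reads 0.5002 (P = 20, f = 5%) to 0.502 (P = 100, f = 10%).
- Older males, HPV-18: T = 402.6/2 = 201.3. The ratio reads 0.5024 to 0.5206.

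Across these two cases a true 0.50 reads as 0.500 to 0.521.

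**5. Exploratory seropositivity.** The cut-offs are 20 mMU/ml (HPV-16) and 24 mMU/ml (HPV-18). Against Table 7's healthy values they run from 20/6056.5 = 0.33% to 24/402.6 = 5.96%, so a small addition could carry a seronegative subject over the line. One misclassified subject moves the rate by 100/n points:

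- n = 72: 1.39 points, and 0.05 × 72 = 3.6, so 4 subjects reach the 5-point margin.
- n = 82: 1.22 points, and 0.05 × 82 = 4.1, so 5 subjects reach it.
- n = 50 (9vHPV, assuming the 200 split equally): 2.0 points, and 0.05 × 50 = 2.5, so 3 subjects exceed it.

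**The case against.** **Purpose of the Dose 1 item.** The protocol gives no reason for the washout. Dose 1 is the only dose visit with a blood draw, so an item found only there may be meant to protect the baseline samples. A reader might infer that its absence at Doses 2 and 3 is an oversight; the text does not establish that. This stands, but it does not explain why the Month 7 sample has no comparable protection.

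**Mechanism.** Nothing in the documents says that these products produce a measurable anti-HPV titre in the assay. This stands, and the point is conditional on it.

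**Exposure.** Participants are 12-60 months off therapy, have clinician clearance, and had no immune globulin in the 3 months before entry. Section 2.5.2 describes humoral immunity as mostly normal or near normal at least one year after therapy. A reader might take the 19.0% transplant share in Table 2 as the exposed fraction. It describes potentially eligible patients, not enrolled subjects or users of these products.

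**Existing safeguards.** Medication review and the consultation clause apply at Doses 2 and 3. They name neither product, govern dosing only, and do not extend to the draws or the analysis sets. The visit forms (Appendices 8, 9 and 16) are not shown and may capture these products, but no rule in the text uses such data.

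**Stronger readings the documents do not support.**

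- A reader might expect titres to rise several-fold in affected subjects. Passive antibody adds to a titre. Tripling one that stands at half the healthy value means adding a full healthy value, 402.6 to 6056.5 mMU/ml in Table 7.
- A reader might infer that the predictor analysis in 8.2.2.2 would be weakened. Its cut-off is half the healthy mean, 201.3 to 3028.25 mMU/ml, which small passive amounts would rarely cross.
- A reader might extend the point to off-study HPV doses before Month 24. That is a separate matter. The remark that 9vHPV replaced qHPV concerns product choice, not revaccination of people who completed a series.

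**Conclusion.** The gap in screening, recording and analysis-set rules is confirmed by the text. Its effect is conditional: it needs products given after Day 1 that carry measurable anti-HPV antibody, and the documents give neither the level nor the frequency. Any bias would run toward non-inferiority. For the primary GMT ratio it is probably small, with a true 0.50 read as 0.500 to 0.521 under the additive assumptions above. It could matter more for seropositivity, but only if 4 or 5 otherwise seronegative subjects in a stratum of 72-82 were affected, and 8.2.2.1 labels that outcome exploratory and unpowered. Severity is minor and confidence moderate. A reader should not conclude that the primary non-inferiority result is undermined.

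**What to change.** 1. In 5.4.5, add blood products and immune globulin to the recorded agents. Record them through the actual Month 7 draw, and again for the period before the Month 24 draw.
2. In 7.1 and 8.2.2.1, exclude from the per-protocol titre and seropositivity analyses any sample preceded by such a product within the protocol's own 3-month interval. Report results with and without those subjects.
3. Have the sponsor reconcile the Dose 1, Dose 2 and Dose 3 screening lists, and the differing product wording in 3.3.3 and 5.4.7.4. No clinical rule is proposed here.

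The cost is one item on the visit forms and one sentence in the analysis-set definition. The downside is that a few subjects may leave the per-protocol set.
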